### **7.1.1 Treatment of Symptomatically Stable Patients after RECIST 1.1 Defined Progression**

Patients with symptomatically stable disease may continue treatment after the initial RECIST 1.1 – defined progression, until symptomatic/clinical progression or a second RECIST 1.1 PD assessment (relative to the initial RECIST1.1 progression, for a given study treatment).

Patients who wish to continue study treatment after RECIST1.1 defined progression, should be informed of all other alternative treatment options available to them by the treating physician and sign an additional consent that they wish to continue study treatment. A decision to continue study treatment after initial progression must also be discussed and agreed by the treating physician and the Sponsor.

The criteria for continuing treatment after initial RECIST 1.1-defined progression are as follows:

- Signed patient consent for treatment after progression
- The patient does not have any significant, unacceptable, or irreversible toxicities indicating that continuing treatment will not further harm the patient.

- There is absence of clinical symptoms or signs indicating clinically significant disease progression accompanied by a decline in ECOG performance status >1.
- There is absence of rapid disease progression or threat to vital organs or critical anatomical sites (e.g. central nervous system metastasis, respiratory failure due to tumour compression, or spinal cord compression) requiring urgent alternative medical intervention.
- Study treatment was not on hold/interrupted at time of progression

Patients continuing study treatment after initial RECIST 1.1 defined progression should continue RECIST scans as per the Schedule of Assessments (the next tumour assessment should be at least 4 weeks after the first RECIST 1.1 defined progression and no later than the next regularly scheduled imaging timepoint).

## 7.2 Participant Withdrawal from the Study

- A participant may withdraw from the study at any time at his/her own request, or may be withdrawn at any time at the discretion of the investigator for safety, behavioural, compliance, or administrative reasons. This is expected to be uncommon.
- A participant who considers withdrawing from the study must be informed by the investigator about modified follow-up options (e.g., telephone contact, a contact with a relative or treating physician, or information from medical records).
- If the participant withdraws consent for disclosure of future information, the sponsor may retain and continue to use any data collected before such a withdrawal of consent.
- If a participant withdraws from the study, it should be confirmed if he/she is still agrees for existing samples to be used in line with the original consent. If he/she requests withdrawal of consent for use of samples, destruction of any samples taken and not tested should be carried in line with what was stated in the informed consent and local regulation. The investigator must document the decision on use of existing samples in the site study records and inform the Global Study Team.

## 7.3 Lost to Follow up

A participant will be considered lost to follow-up if he or she repeatedly fails to return for scheduled visits and is unable to be contacted by the study site.

The following actions must be taken if a participant fails to return to the clinic for a required study visit:

- The site must attempt to contact the participant and reschedule the missed visit as soon as possible and counsel the participant on the importance of maintaining the assigned visit

schedule and ascertain whether or not the participant wishes to and/or should continue in the study.

- Before a participant is deemed lost to follow up, the investigator or designee must make every effort to regain contact with the participant (where possible, 3 telephone calls and, if necessary, a certified letter to the participant's last known mailing address or local equivalent methods). These contact attempts should be documented in the participant's medical record.

## 8 STUDY ASSESSMENTS AND PROCEDURES

- Study procedures and their timing are summarised in the SoA. Protocol waivers or exemptions are not allowed.
- Immediate safety concerns should be discussed with the sponsor immediately upon occurrence or awareness to determine if the participant should continue or discontinue study intervention.
- Adherence to the study design requirements, including those specified in the SoA, is essential and required for study conduct.
- All screening evaluations must be completed and reviewed by Investigator to confirm that potential participants meet all eligibility criteria. The investigator will maintain a screening log to record details of all participants screened and to confirm eligibility or record reasons for screening failure, as applicable.
- Procedures conducted as part of the participant's routine clinical management (e.g., blood count) and obtained before signing of the ICF may be utilised for screening or baseline purposes provided the procedures met the protocol-specified criteria and were performed within 28 days of the first dose of study treatment.
- The maximum amount of blood collected from each participant over the duration of the study, is expected to not exceed 500 mL.

### 8.1 Efficacy Assessments

The primary endpoint for the RXC004 monotherapy arm, will be the DCR using a patients best overall response, with secondary endpoints of % change in the sum of target lesions, ORR, DoR, PFS and OS. For the RXC004 + nivolumab arm, the primary endpoint will be ORR using a patients BOR with secondary endpoints of % change in the sum of target lesions, DCR, DoR, PFS and OS.

Efficacy assessments of DCR, ORR, % change in the sum of target lesions, DoR and PFS will be derived using investigator RECIST 1.1 assessments. In addition, OS will also be evaluated.

#### 8.1.1 Tumour assessments

Tumour assessments utilize images from CT or MRI, collected during screening/baseline and at regular (follow-up) intervals during the study. The same imaging method should be used throughout the study. It is important to follow the tumour assessment schedule as per the SoA. Tumour assessments will continue until RECIST1.1-defined radiological progression. Patients treated with RXC004+nivolumab that continue treatment after RECIST1.1 progression, will continue tumour assessments until second RECIST1.1 defined radiological progression (relative to the initial RXC004+nivolumab progression event).

Sites will be required to store electronic copies of all scans, and the Sponsor may arrange for possible centralised storage of all imaging data. Centralised storage of imaging data would be possible to support an independent centralized review of disease assessments.

In addition, if available, the last 2 imaging scans taken prior to the screening scan for this study and/or their reports should be kept for possible central/sponsor review.

### **8.1.2      Survival assessments**

Assessments for survival must be made following treatment discontinuation, as indicated in the SoA. Survival information may be obtained via telephone contact with the patient or the patient's family, or by contact with the patient's current physician. The details of first and subsequent therapies for cancer, after discontinuation of treatment, will be collected. In addition, patients on treatment or in survival follow-up will be contacted within 7 days of the DCO for any survival analyses to provide complete survival data.

## **8.2      Safety Assessments**

### **8.2.1      Clinical Safety Laboratory Assessments**

Blood samples for determination of clinical chemistry and haematology will be taken at the visits indicated in the SoA. Additional safety samples may be collected if clinically indicated at the discretion of the investigator. The date, time of collection and results (values, units and reference ranges) will be recorded on the appropriate eCRF.

The clinical chemistry and haematology will be performed at a local laboratory at or near to the investigator site. Sample tubes and sample sizes may vary depending on laboratory method used and routine practice at the site.

The following laboratory variables will be measured.

**Table 16      Laboratory safety variables**

Haematology/Haemostasis (whole blood)	Clinical Chemistry (serum or plasma)
Haemoglobin (Hb)	Creatinine and creatinine clearance a
Total white cell count	Bilirubin, total
Neutrophils (absolute count or %)	Alkaline phosphatise (ALP)
Platelet count	Aspartate transaminase (AST)
Lymphocytes (absolute count or %)	Alanine transaminase (ALT)
	Albumin
	Potassium
Other tests:	Calcium, total
HIV antibodies c	Phosphate
Hepatitis B surface antigen c	Sodium
Hepatitis C antibodies c	Glucose
	Thyroid-stimulating hormone (TSH)
	Lipase
	Lactate dehydrogenase (LDH)
	Amylase
	T3 free (reflex) b
	T4 free (reflex) b
	C-reactive protein (CRP)
	Vitamin D c

a Creatinine clearance at baseline only

b Free T3 or T4 only need to be measured if TSH is abnormal or if Investigator judges that there may be an AE related to the endocrine system

c Required at baseline/screening only.

### 8.2.2      Physical Examinations

A physical examination will include, at a minimum, assessments of the skin, lungs, cardiovascular system, and abdomen (liver and spleen). A neurological exam should also be conducted at screening/baseline and thereafter as clinically indicated.

Physical examinations will be performed at timelines as specified in the SoA,

### 8.2.3      Vital Signs

The following vital signs will be performed at timelines as specified in the SoA;

- Blood pressure

- Pulse rate
- Temperature
- Respiration rate
- Weight
- Height (recorded at baseline only)

#### **8.2.4      Electrocardiograms**

Triplet 12-lead ECGs will be performed at timepoints as specified in the SoA. ECGs should be obtained after the patient has been in a supine position for 5 minutes and recorded while the patient remains in that position. Mean QT intervals corrected for heart rate should be calculated using Fridericia's formula (QTcF).

All ECG traces should be kept by site for possible central/sponsor review.

At selected sites, digital ECG collection may take place using ambulatory Holter monitoring equipment for approximately 24 hours on Cycle 0 Day 1 and Cycle 1 Day 15. The information will be stored and analysed centrally.

#### **8.2.5      ECOG performance status**

ECOG performance status will be assessed at the times specified in the assessment schedules based on the following:

0. Fully active; able to carry out all usual activities without restrictions
1. Restricted in strenuous activity, but ambulatory and able to carry out light work or work of a sedentary nature (e.g. light housework or office work)
2. Ambulatory and capable of self-care, but unable to carry out any work activities; up and about more than 50% of waking hours
3. Capable of only limited self-care; confined to bed or chair more than 50% of waking hours
4. Completely disabled; unable to carry out any self-care and totally confined to bed or chair
5. Dead

#### **8.2.6      Other Safety Assessments**

## Pregnancy tests

All women of childbearing potential will have pregnancy tests (urine or serum) performed at timepoints as specified in the SoA

## Screening safety tests

Tests for hepatitis B surface antigen, hepatitis C antibodies, and HIV antibodies will be performed for all patients at screening.

## 8.3 Adverse Events and Serious Adverse Events

The Principal investigator (PI) is responsible for ensuring that all staff involved in the study are familiar with the content of this section.

The definitions of an AE or SAE can be found in Appendix B.

AEs will be reported by the patient (or, when appropriate, by a caregiver, surrogate, or the participant's legally authorised representative).

The investigator and any designees are responsible for detecting, documenting, and recording events that meet the definition of an AE.

### 8.3.1 Time Period and Frequency for Collecting AE and SAE Information

Adverse Events will be collected from time of signature of the main study informed consent form throughout the treatment period and until 30 days after the last dose of RXC004 (for patients treated with RXC004 monotherapy only) or 90 days after the last dose of nivolumab (for patients treated with RXC004 and nivolumab).

SAEs will be recorded from the time of signing of the main study informed consent form until the follow-up period is completed (30 days after the last dose of RXC004 [for patients treated with RXC004 monotherapy only] or 90 days after the last dose of nivolumab [for patients treated with RXC004 and nivolumab]). If an event starts after the safety follow-up period defined above is considered to be a late-onset toxicity related to study treatment, then it should be reported as an AE or SAE, as applicable.

If the investigator becomes aware of a serious adverse event with a suspected causal relationship to the investigational medicinal product that occurs after the end of the clinical study in a participant treated by him or her, the investigator shall, without undue delay, report the serious adverse event to the sponsor.

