### 2.3.2 Nivolumab Risks

Checkpoint inhibitors including anti PD-1, as well as antibodies directed against PDL-1 and CTLA-4, boost the endogenous immune responses directed against tumours. Adverse events seen with checkpoint inhibitors are frequently due to immune mediated mechanisms and can occur in any organ system. The adverse events known to occur with nivolumab treatment (as monotherapy and in combination with various agents) are well documented (Haanen et al 2017) and include gastrointestinal effects (e.g. diarrhoea or colitis), pneumonitis, hepatic events, skin rashes myocarditis and endocrinopathies (including hypo and hyper-thyroidism).

The safety of nivolumab administered as a single agent or in combination with ipilimumab in patients with mCRC was evaluated in the CHECKMATE-142 study. (NCT02060188). The most frequent serious adverse reactions reported in at least 2% of patients treated with nivolumab monotherapy were colitis/diarrhoea, hepatic events, abdominal pain, acute kidney injury, pyrexia, and dehydration. The most common adverse reactions for single agent nivolumab (reported in at least 20% of patients) were fatigue, diarrhea, pyrexia, musculoskeletal pain, abdominal pain, pruritus, nausea, rash, decreased appetite, and vomiting (Overman et al 2017).

Immune mediated adverse events that can occur during treatment with nivolumab can be seen weeks or months after discontinuation of treatment. Symptoms of these events will be monitored throughout treatment (e.g. diarrhoea, rash, and neuropathy). Laboratory assessments will check for elevated liver enzymes, kidney and thyroid function, electrolytes, glucose and blood counts.

More detailed information about the known and expected benefits and potential risks of nivolumab may be found in the nivolumab Package Insert.

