#### **9.4.3.1 Adverse events**

Treatment emergent AEs (TEAEs) are defined as those AEs with an onset after dosing and those pre-existing AEs that worsen after the start of dosing and within 30 days of stopping RXC004 monotherapy or 90 days after the last actual nivolumab dose (for patients on RXC004 and nivolumab combination). For AEs, verbatim terms in the eCRF will be mapped to preferred terms and system organ class using the Medical Dictionary for Regulatory activities (version 22.0 or later) CTCAE criteria v5.0 will be used to grade the severity of AEs. The incidence of treatment emergent AEs will be summarised by preferred term and system organ class as well as severity. Treatment related TEAEs will be summarised in the same way. Subject incidence of SAEs will also be produced.

By subject listings of all AEs, deaths, SAEs and TEAEs leading to discontinuation will also be produced.

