4.12.1 Adverse Events

Adverse Events will be collected from time of signature of informed consent form throughout the treatment period and until 30 days after the last dose of RXC004 (for patients treated with RXC004 monotherapy only) or 90 days after the last dose of Nivolumab (for patients treated with RXC004 and Nivolumab).

SAEs will be recorded from the time of signing of informed consent form until the follow-up period is completed: 30 days after the last dose of RXC004 (for patients treated with RXC004 monotherapy only) or 90 days after the last dose of Nivolumab (for patients treated with RXC004 and Nivolumab).

The following variables will be collected for each AE:

- AE (verbatim)
- Start/Stop date
- CTCAE grade at onset and grade changes
- Seriousness
- Investigator causality rating against the Investigational Product(s)
- Action taken with regard to Investigational Product(s)
- Action taken with regards to AE

- Outcome

In addition, the following variables will be collected for SAEs:

- Date AE met criteria for SAE
- Date investigator became aware of SAE
- Hospitalisation
- Life Threatening
- Congenital Anomaly or Birth Defect
- Disability or Permanent Damage
- Other Medically Important Serious Event
- Date of hospitalisation
- Date of discharge
- Causality assessment in relation to Study procedure(s)
- Causality assessment to other medication

Partially complete AE dates will not be imputed in the listings and the available day, month and year components will be used to determine if an adverse event is treatment- emergent taking the first dosing date last treatment date as references.

More specifically:

- Start date of AE missing: Assumed to be date of first treatment dose.
- Start day and month of AE missing: Assumed to be date of first treatment dose (if same year for both dates), January 1st otherwise.
- Start day of AE missing: Assumed to be date of first treatment dose (if same month and year for both dates), first day of the month otherwise.
- End date for non-ongoing AE missing: Assumed to date of last treatment dose
- End day and month for non-ongoing AE missing: Assumed to be date of last treatment dose (if same year for both dates), December 31st otherwise.
- End day for non-ongoing AE missing: Assumed to be date of last treatment dose (if same month and year for both dates), last day of the month otherwise.

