Explain if first use TEAEs with missing relationship to the study drug will be considered as related. AEs will be coded using the MedDRA, latest version. Grading will be performed using CTCAE version 5.0.

TEAEs are defined as those AEs with an onset after dosing and those pre-existing AEs that worsen after the start of dosing and within 30 days of stopping RXC004 monotherapy or 90 days after the last actual Nivolumab dose (for patients on RXC004 and Nivolumab combination).

An overview table of TEAEs will be provided showing the number of patients, the percentage of patients and the number of events for the following categories of events:

- Any TEAE
- Any treatment related TEAE to RXC004
- Any treatment related TEAE to Nivolumab
- Any grade ≥ 3 TEAE
- Any grade ≥ 3 TEAE related to RXC004
- Any grade ≥ 3 TEAE related to Nivolumab
- Any serious TEAE (STEAE)
- Any serious TEAE related to RXC004
- Any serious TEAE related to Nivolumab
- Any TEAE leading to death
- Any TEAE leading to permanent discontinuation or reduction or interruption of RXC004
- Any TEAE leading to permanent discontinuation of RXC004
- Any TEAEs leading to RXC004 reduction
- Any TEAEs leading to RXC004 interruption
- Any TEAE leading to permanent discontinuation or interruption of Nivolumab
- Any TEAE leading to permanent discontinuation of Nivolumab
- Any TEAEs leading to Nivolumab interruption

For TEAEs, TEAEs considered related (RXC004 and Nivolumab), STEAEs, STEAEs considered related (RXC004 and Nivolumab), TEAEs leading to study treatment discontinuation, TEAEs leading to RXC004 reduction, TEAEs leading to RXC004 interruption, TEAEs leading to Nivolumab interruption, TEAEs by maximum grade, TEAEs with grade ≥ 3 , TEAEs with grade ≥ 3 related to RXC004, TEAEs with grade ≥ 3 related to Nivolumab, death, detailed tables will be created showing the number of patients who experienced at least one TEAE, the corresponding percentage of patients and the number of events by SOC and PT.

SOC will be sorted by alphabetical order. PTs, within each SOC, will be sorted by descending order of total frequency. In the event of PTs with equal total frequencies, the relevant PTs will be sorted

alphabetically.. In addition, a table summarizing TEAEs by decreasing frequency of Preferred Terms will be produced for all TEAEs and TEAEs related to RXC004/Nivolumab.

A table will also be produced showing the details for every patient that die (death date, cause of death etc...).

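### The SAP's AE incidence tables count only TEAEs, so non-fatal late-onset related events that Protocol 8.3.1 requires to be reported are listed but enter no incidence count

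*Protocol*

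**What the plan says.** **Reporting duty.** Protocol 8.3.1 collects AEs and SAEs from main consent to 30 days after the last RXC004 dose for monotherapy-only patients, or 90 days after the last nivolumab dose for combination patients. It then adds that an event starting after that period and "considered to be a late-onset toxicity related to study treatment, then it should be reported as an AE or SAE, as applicable".

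**Collection period in the SAP.** SAP 4.12.1 restates the period ("SAEs will be recorded from the time of signing of informed consent form until the follow-up period is completed", with the same 30 and 90 days) but does not repeat the late-onset sentence.

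**TEAE definition.** SAP 4.12.1 covers AEs that begin once treatment has started and earlier AEs that then become worse, and its time limit reads "within 30 days of stopping RXC004 monotherapy or 90 days after the last actual Nivolumab dose". Protocol 9.4.3.1 has the same limit: "within 30 days of stopping RXC004 monotherapy or 90 days after the last actual nivolumab dose". Neither mentions the late-onset events of 8.3.1.

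**Tables.** The SAP 4.12.1 overview counts TEAEs: any, related to each drug, grade 3 or higher, serious, fatal, and those leading to a change in treatment. The system organ class and preferred term tables are described as "showing the number of patients who experienced at least one TEAE".

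**Other outputs.** SAP 4.12.1 also plans a listing of every AE, treatment-emergent or not, with onset date, grade, seriousness and causality; a listing of serious TEAEs; and a table of details for every death. Protocol 9.4.3.1 promises a per-subject SAE incidence, without saying that it is limited to treatment-emergent SAEs.

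**The concern.** The protocol asks sites to report a specific class of events after the window closes, and the analysis plan gives that class no count. These are the events that have been judged related to study treatment, so leaving them out can only lower the number of patients shown with a related event; it can never raise it. The protocol expects such events: Protocol 2.3.2 says that immune-mediated events with nivolumab "can be seen weeks or months after discontinuation of treatment". For monotherapy-only patients the window is 30 days, and Protocol 8.3.13 names bone toxicity and colitis as events of potential interest for RXC004.

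At stake is the secondary safety endpoint, which in both documents is the incidence of AEs and SAEs and not of TEAEs alone. A line in a listing is not an incidence. A reader of the report who looks only at the summary tables would not learn that a late related SAE had occurred.

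**Working it through.** The documents state no figure on this point, so there is none to reproduce. The check follows one hypothetical event through the plan: a non-fatal, related SAE with first onset after day 30 (monotherapy only) or day 90 (combination).

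1. **Is it reported?** Yes. Protocol 8.3.1 requires it.
2. **Is it a TEAE?** On the ordinary reading, no. The definition ends at the same 30 or 90 days, with no exception. The wording can be parsed another way: the limit could attach only to pre-existing AEs that worsen, in which case a new late event would qualify. But when SAP 4.12.1 explains how partial dates are classified, it uses both the first and the last treatment dates as reference points. That suggests an end limit is meant for AEs generally.
3. **Is it in an AE incidence table?** No. The overview and the system organ class and preferred term tables count TEAEs or serious TEAEs.
4. **Is it in the serious-event listing?** No. That listing covers serious TEAEs.
5. **Is it in the all-AE listing?** Yes, with seriousness and causality.
6. **Is it in the death table?** Only if the patient dies. That table has no window.
7. **Does Protocol 9.4.3.1 provide a count?** Its SAE incidence has no stated TEAE limit, so the event would be included. The SAP replaces this with serious-TEAE tables, and the readable text of SAP 4.15, which records departures from the protocol, does not mention the narrowing.

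The result does not depend on which drug's last dose closes the window, because under either choice the event falls after it.

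**Size, for illustration only.** Let k be the number of patients whose only related SAE falls after the window, and n the number dosed in the arm. The change in related-SAE incidence is k / n. With k = 1 and n = 20 (the planned evaluable number per arm), 1/20 = 5 percentage points. The tables use the full analysis set; if more than 20 are dosed in an arm, the figure is smaller. If the patient already has a related SAE inside the window, the change is zero.

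**The case against.** The strongest reply is that a fixed TEAE window is sound practice and matches the period of active collection. In the schedules of assessments, AE collection ends with the 30- and 90-day follow-up visits; the later survival contacts collect survival status and subsequent therapy. Events after that depend on unsolicited reports and on how long each patient is followed. An incidence over a defined window is not biased because it leaves out events outside the window. Admitting late events to the TEAE definition only when judged related would give related events an open-ended window and unrelated events a closed one, and would mix active with passive ascertainment. This stands, and it is why the TEAE definition should not be widened.

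It is also fair to say that the 90-day window already covers much of the delay that Protocol 2.3.2 describes, that the protocol and not the SAP governs collection (so the sentence missing from the SAP loses no event), and that in arms of about 20 with no formal comparison a few late events can be read from the listing. These points limit the importance of the gap. They do not supply the count that the endpoint and Protocol 9.4.3.1 call for.

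A reader might infer two stronger things, and the documents support neither. The first is that every safety table in the SAP is TEAE-based: the laboratory, vital-sign, ECG and ECOG tables are not, and the death table covers every death. The second is that late related events are lost: they are in the all-AE listing with seriousness and causality. They are untabulated, not unreported.

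**Conclusion.** The point holds in a limited form. On the ordinary reading of the TEAE sentence, non-fatal late-onset related AEs and SAEs that the protocol requires to be reported appear in one listing and in no incidence count. This falls short of an endpoint defined as the incidence of AEs and SAEs, and of the SAE incidence promised in Protocol 9.4.3.1. If the sentence is read the other way, new late events are counted with no end limit. The ambiguity is then itself the defect, since two programmers could produce different related-SAE rates from the same data.

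The size is unknown because the documents give no rate of late events. The 5 points rest on one affected patient, 20 dosed, and no related SAE in that patient inside the window. It is tempting to compare this with the Phase 1 combination result in Protocol Table 9, where 1 of 13 patients (8%) had a serious treatment-related TEAE. That comparison does not work: the Phase 1 figure used a window of 30 days after the last dose, so it says nothing about late events and is not an expected rate for this study. Nor do the documents support saying that the related-event rates are materially biased. This is a worthwhile and cheap improvement, not a flaw that threatens the safety conclusions.

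**What to change.** Three changes in SAP 4.12.1:

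1. Keep the fixed-window TEAE tables as they are.
2. Add one table by arm (A, B, A1 and A2) giving the number of patients with AEs, and with SAEs, that start after the window and are reported under Protocol 8.3.1 as related to RXC004 or nivolumab. Flag these events in the data and label the table as passively ascertained, so that it is not read as a rate over a common follow-up period.
3. State that the 30- or 90-day limit applies both to new-onset AEs and to pre-existing AEs that worsen.

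The cost is one flag, one sentence and one small table whose follow-up differs between patients. No new visits or assessments are needed. One caution: Protocol 6.7 moves SAE reporting to paper forms for patients who continue treatment after the data cut-off, so the table should state the data source and cut-off that it covers.
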